8.4.8 Medication errors or misuses of medicinal product

All reports of medication error or misuse in relation to the IMP with or without an AE must be recorded on the corresponding page(s) of the CRF and transmitted to the Sponsor's representative following standard processes.

A medication error is an unintended failure in the drug treatment process (ie, mistake in the process of prescribing, storing, dispensing, preparing, or administering medicinal products in clinical practice) that leads to, or has the potential to lead to harm to the participant. This includes situations in which a participant was involved or not (eg, even if the error was recognized and intercepted before the participant received or used the product), and whether it resulted in harm to the participant or not.

A misuse refers to situations where the medicinal product is intentionally and inappropriately used, ie, not in accordance with the terms of the marketing authorization or outside what is foreseen in the protocol, by the participant for a therapeutic purpose.

Of note, if a medication error or misuse meets the protocol definition of an overdose, it will be recorded in the overdose page of the eCRF.

8.4.9 Guidelines for reporting product complaints

Any defect in the IMP/AxMP must be reported as soon as possible by the Investigator to the monitoring team that will complete a product complaint form within required timelines.

Appropriate information (eg, samples, labels or documents like pictures or photocopies) related to product identification and to the potential deficiencies may need to be gathered. The Investigator will assess whether or not the quality issue has to be reported together with an AE or SAE.

8.5 PHARMACOKINETICS

Blood samples will be collected for determination of functional itepekimab concentrations in serum as specified in the SoA ([Section 1.3](#)). Samples may be collected at additional time points during the study if warranted (see Appendix 6, [Section 10.6](#)). Special procedures for collection, storage, and shipping of serum are described in separate operational manuals. The actual date and time (24-hour clock time) of each sample will be recorded. The sample types for PK samples are described in [Table 9](#).

Table 9 - Summary of handling procedures for PK samples

Sample type	PK (itepekimab)
Matrix	Serum
Blood sample volume	5 mL
Blood handling procedures	See Operational Manual
Serum aliquot split	2 aliquots
Serum shipment condition	In dry ice

Abbreviations: PK = pharmacokinetic(s).

The bioanalytical methods for PK are summarized in [Table 10](#).

Table 10 - Summary of bioanalytical methods for PK samples

Analyte	PK (itepekimab)
Matrix	Serum
Analytical technique	ELISA
Site of bioanalysis	Regeneron

Abbreviations: ELISA = enzyme-linked immunosorbent assay; PK = pharmacokinetic(s).

Drug concentration information that may unblind the study will not be reported to investigative sites or blinded personnel until the study has been unblinded.

Note: If an SAE or AESI (anaphylaxis, systemic hypersensitivity reaction, and severe ISR lasting 24 hours) occurs in a participant, additional blood samples may be collected for determination of functional itepekimab concentration at or near the onset of the occurrence of the event.

An unscheduled systemic drug concentration page in the eCRF must be completed as such a case as well.

Any changes in the timing or addition of time points for any planned study assessments must be documented and approved by the relevant study team member and then archived in the Sponsor and site study files but will not constitute a protocol amendment. The IRB/IEC will be informed of any safety issues that require alteration of the safety monitoring scheme or amendment of the ICF.

- Pharmacokinetic samples could be used for testing analytical method performance such as comparability and incurred sample reproducibility and for possible exploratory analysis of drug metabolites. The exploratory data will not be included in the study report but will be kept on file.

For China, please see [Section 10.8.1](#) for details.

8.6 PHARMACODYNAMICS

See [Section 8.8](#)

8.7 GENETICS

A whole blood sample for exploratory DNA analysis will be collected from participants eligible for enrollment, who have consented to participate in the optional genetic analysis component of the study. Participation is optional in this blood-based DNA analysis. Participants who do not wish to participate in the genetic research may still participate in the study. Whole blood samples for DNA analysis will be collected at pre-dose baseline. In the event of DNA extraction failure, a replacement genetic blood sample may be requested from the participant. Signed informed consent will be required to obtain a replacement sample unless it was included in the original consent.

A nasal brushing sample taken from the inferior turbinate of each nostril will be collected for exploratory RNA analysis from participants eligible for enrollment. Participants have the option to opt out from participation in providing nasal brushing samples.

Samples collection is indicated in the SoA ([Section 1.3](#)).

Whole blood DNA samples and nasal brushing RNA samples may be used to determine a possible relationship between gene expression levels and/or genetic variation and

- Response to treatment with itepekimab (which may include aspects such as biologic effects and clinical efficacy).
- How the body processes itepekimab.
- Possible side effects of itepekimab.
- Features of CRSwNP and related diseases.

Analysis of nasal brushing RNA will also be performed to identify changes in gene expression from baseline and identify potentially predictive and response-associated gene signatures.

Details on handling, shipping, and destruction of samples for genetic analysis is described in a separate document except where not applicable due to country-specific requirements.

Results of these exploratory analyses may be presented in reports separate from the CSR.

More information regarding genetic research can be found in Appendix 5 ([Section 10.5](#)).

For China, please see [Section 10.8.1](#) for details.

8.8 BIOMARKERS

- Blood samples will be collected to perform analysis of markers associated with CRSwNP and/or itepekimab activity to determine the effect of itepekimab on the biomarkers. Biomarkers may include and are not limited to total IgE, TARC, eotaxin3, periostin, ECP, IL5, IL13, IFN γ , IL17A, IL33, sST2. Samples will be collected according to the schedule described in the SoA and as detailed in the laboratory manual provided separately to the sites. Analysis will be stepwise and depending upon outcome some analyses may be skipped.
- Blood eosinophils, neutrophils, and monocytes will be assessed pre-dose and at time points described in the SoA (see [Section 1.3](#)).
- Samples for analysis of nasal absorption biomarkers will be collected, which may include and are not limited IFN γ , IL5, IL17A, IL33, TNF α , IL17F, IL22, IL13, CXCL8 (IL8), IL4, IL6, IL1 β , tryptase, CXCL9, CXCL10, colony stimulating factor (CSF)3. Analysis will be stepwise and depending upon outcome some analyses may be skipped.
- Nasal brushing for analysis on gene expression changes will be assessed at selected time points described in the SoA.
- Urine biomarkers: leukotriene E4 (LTE4) and creatinine.

For China, please see [Section 10.8.1](#) for details.

8.9 IMMUNOGENICITY ASSESSMENTS

Antibodies to itepekimab will be evaluated in serum samples collected from all participants according to the SoA ([Section 1.3](#)). Additionally, serum samples should also be collected at the final visit from participants who discontinued study intervention or were withdrawn from the study.

Instructions for the collection and handling of these samples will be provided by the Sponsor. These samples will be tested by the Sponsor or Sponsor's designee using a validated assay method.

Samples for immunogenicity analyses and their derivatives may be stored for up to 5 years after last patient last visit (LPLV) for potential re-analyses.

A 3-tiered approach will be employed to assess the immunogenicity of itepekimab when applicable: samples will be screened and then confirmed for antibodies binding to itepekimab and the titer of confirmed positive samples will be reported. Other analyses may be performed to further characterize the immunogenicity of itepekimab.

All samples collected for detection of antibodies to itepekimab may also be evaluated for itepekimab serum concentration to enable interpretation of the antibody data.

For China, please see [Section 10.8.1](#) for details.

8.10 HEALTH ECONOMICS OR MEDICAL RESOURCE UTILIZATION AND HEALTH ECONOMICS

For all participants throughout the study, the Investigator and study site personnel will collect data about health care resource utilization associated with medical encounters that are related to CRSwNP and asthma for participants with asthma co-morbidity. Protocol-mandated procedures, tests, and encounters are excluded.

The data collected will include the number of outpatient/specialist encounters and emergency room/urgent care clinic visits.

The Sponsor may use the collected data to conduct economic analyses. Hospitalization and CRS-related surgery data are collected per protocol in other sections and thus will not be collected again but can inform economic analyses.

8.11 USE OF BIOLOGICAL SAMPLES AND DATA FOR FUTURE RESEARCH

Future research may help further the understanding of disease and the development of new medicines. Reuse of coded data and biological samples (leftover and additional) collected as part of the study will be limited to future scientific research conducted under a research plan for the purpose of diagnosing, preventing or treating diseases. The future research projects will be conducted under the Sponsor's and/or its affiliates' and/or, if applicable, the partner of

the Sponsor which has licensed the study drug to the Sponsor or which is co-developing the study drug with the Sponsor's control, acting alone or in collaboration with research partners such as universities, research institutions or industrial partners with whom the coded study data may be shared.

Coded study data and biological samples will be stored and used for future research only when consented to by participants (see [Section 10.1.3](#)) and, when applicable, further information on the future research has been provided to the study participant unless prohibited by local laws or IRBs/IECs (in such case, consent for future use of data/sample will not be included in the local ICF). The conditions for reuse will be adapted locally with the appropriate language in the ICF.

In any case, a specific consent will be collected for the performance of genetic analyses on leftover and/or additional samples.

For China, please see [Section 10.8.1](#) for details.

Data protection – Processing of coded study data

The study participant will be provided with all mandatory details of the data processing in Part 2 of the core ICF.

The Sponsor adopts safeguards for protecting participant confidentiality and personal data (see [Section 10.1.4](#)).

Use of leftover samples and additional samples for future research

Remaining leftover samples will be used only after the study ends, ie, EOS as defined in the study protocol. Additional/extra samples can be collected and used during the study conduct at a given timepoint (eg, at randomization Visit) as defined in the study protocol.

The study participant will be provided with all mandatory details of the use of the human biological samples (leftover and additional) in Part 2 of the core ICF.

Study participant data will be stored for up to 25 years for regulatory purposes. Biological samples for future use will be stored for up to 25 years after the EOS unless local regulations require a different retention period. Any samples remaining at the end of retention period will be destroyed. If a participant requests destruction of his/her samples before the end of the retention period, the Investigator must notify the Sponsor (or its contract organization) in writing. In such case, samples will be destroyed and related coded data will be anonymized unless otherwise required by applicable laws.

9 STATISTICAL CONSIDERATIONS

The statistical analysis plan will be finalized prior to interim analysis and database lock and it will include a more technical and detailed description of the statistical analyses described in this section. This section is a summary of the planned statistical analyses of the most important endpoints including primary and key secondary endpoints.

9.1 POPULATIONS FOR ANALYSES

The following populations for analyses are defined.

Table 11 - Populations for analyses

Population	Description
Screened	All participants who signed the ICF.
Randomized	All participants from screened population who have been allocated to a randomized intervention by IRT regardless of whether the intervention was received.
Exposed	All screened participants who have taken at least 1 dose of study intervention regardless of the amount of study intervention administered.
ITT/Efficacy	All randomized participants. Participants will be analyzed according to the intervention allocated by randomization.
Safety	All randomized participants who have taken at least 1 dose of study intervention, regardless of the amount of intervention administered. Participants will be analyzed according to the intervention they actually received.
PK	All participants from the safety population with at least one post-baseline PK result. Participants will be analyzed according to the intervention they actually received.
ADA	All participants from the safety population treated with itepekimab with at least one post-baseline ADA result (positive, negative or inconclusive). Participants will be analyzed according to the intervention they actually received.

Abbreviations: ADA = antidrug antibody; ICF = informed consent form; IRT = interactive response technology; ITT = intent-to-treat; PK = pharmacokinetics.

Participants exposed to study intervention before or without being randomized will not be considered randomized and will not be included in any analysis population. The safety experience of these participants will be reported separately.

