
 To evaluate the efficacy of itepekimab compared to placebo. To evaluate the safety and tolerability of itepekimab compared to placebo in participants with CRSwNP. To evaluate the PK of itepekimab. Assessment of immunogenicity to itepekimab over time compared to placebo. 	
 Annualized rate of SCS course or surgery for CRS during the planned study intervention period in participants with AERD. Time to first either SCS or surgery for CRS in participants with AERD. Change from baseline to Weeks 24 and 52 in pre-BD FEV1 (in mL) in participants with AERD. Proportion of NPS responders at Weeks 24 and 52 (defined as participants with improvement by at least 1 point in NPS). Proportion of NPS responders at Weeks 24 and 52 (defined as participants with improvement by at least 2 points in NPS). Incidence of TEAEs, TESAEs, TEAESIs and TEAEs leading to treatment discontinuation. Itepekimab concentration in serum. Incidence of treatment-emergent anti-itepekimab antibody (ADA) responses throughout the study.
Tertiary/Exploratory	

 To evaluate the effect of itepekimab on overall health status, cough, PGIS and PGIC. To evaluate the efficacy of itepekimab compared to placebo in CRSwNP quality of life. To evaluate the effects of itepekimab compared to placebo on total sinus opacification. To evaluate the effect of itepekimab on health care resource use/productivity compared to placebo. To evaluate the early effect of itepekimab compared to placebo on lung function and asthma in the subgroup of participants with co-morbid asthma. 	
 Change from baseline to Weeks 24 and 52 in the EQ-5D index and VAS. Change from baseline to Weeks 24 and 52 in PGIS score for each symptom and for symptoms overall. PGIC score at Weeks 24 and 52 for each symptom and for symptoms overall. Change from baseline to Weeks 24 and 52 in Leicester Cough Questionnaire total score. Proportion of SNOT-22 responders at Weeks 24 and 52 (defined as participants with improvement of at least 8.9 points in SNOT-22). Change from baseline to Week 24 in sinus (all sinuses) percent opacification volume assessed by CT scan. Cumulative number of health care resource utilization by visit type. Change from baseline to Weeks 24 and 52 in WPAI-SHP on overall work impairment and daily activity impairment. Change from baseline to Weeks 4 in pre-BD FEV1.

Objectives	Endpoints

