9.2.7 Other analyses

Analyses of PK and immunogenicity will be described in the SAP.

For a regional or national emergency declared by a governmental agency, contingency measures are included in Appendix 9 ([Section 10.9](#): Contingency measures for a regional or national emergency that is declared by a governmental agency).

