9.4 SAMPLE SIZE DETERMINATION

Approximately 210 participants will be randomized in 1:1:1 ratio to investigational intervention groups.

The sample size calculations are based on the co-primary endpoints NPS and NCS. The planned sample size is approximately 70 participants per study intervention group. With a two-sample t-test at a two-sided significance level of $\alpha = 0.049$, this sample size will provide:

- 95% power to detect a -1.10 difference for change from baseline in NPS at Week 24 between itepekimab and placebo and a common SD of 1.79. The minimal detectable difference is around -0.60.
- 95% power to detect a -0.55 difference for change from baseline in NCS at Week 24 between itepekimab and placebo and a common SD of 0.9. The minimal detectable difference is around -0.30.

The combined power of the 2 co-primary efficacy endpoints is at least 90% assuming no negative correlation between the 2 endpoints.

Differences of -1.10 and -0.55 in NPS and NCS from placebo are considered clinically relevant (54). The common SDs were estimated from LIBERTY NP SINUS-24 and SINUS-52 trials with dupilumab (NCT02912468; NCT02898454).

For the key secondary endpoints of change from baseline in NPS and NCS at Week 52, the study will have a 95% power to detect the same treatment differences as for the co-primary endpoints with the same assumed common SDs based on a two-sided α level of 0.049.

Note that as the primary analyses will be performed based on the ITT population with the dropouts (ie, one of the intercurrent events) handled using the treatment policy strategy and missing data imputed using the MI method, the sample size calculations were performed on all randomized participants. In other words, the detectable treatment differences stated above are for ITT population including early dropouts. Very low dropout rates (<5%) were observed from LIBERTY NP SINUS-24 and SINUS-52 studies (NCT02912468; NCT02898454), therefore the impact on the treatment effects is expected to be minimal.

Calculations were made based on two-sample t-test using nQuery Advisor 9.2.1.0.

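### Table 11 limits the ADA population to itepekimab-treated participants, which contradicts the secondary objective of comparing immunogenicity with placebo and the sampling of all arms

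*Protocol*

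**What the plan says.** The relevant statements are all in the protocol.

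- **Objective.** The synopsis and Table 2 (section 3) list the same secondary objective: "Assessment of immunogenicity to itepekimab over time compared to placebo".
- **Endpoint.** The endpoint paired with it is "Incidence of treatment-emergent anti-itepekimab antibody (ADA) responses throughout the study".
- **Sampling.** Section 8.9 states: "Antibodies to itepekimab will be evaluated in serum samples collected from all participants according to the SoA". The ADA row of the Schedule of Activities (section 1.3) has no restriction by arm. It shows a Week 0 sample and further samples at Weeks 12, 24, 52 and 72, and its footnote requires collection before dosing.
- **Population.** Table 11 (section 9.1) defines the ADA population as "All participants from the safety population treated with itepekimab with at least one post-baseline ADA result (positive, negative or inconclusive"), analysed by the intervention actually received. In the row above, the PK population is "All participants from the safety population with at least one post-baseline PK result", with no active-only limit.
- **Methods.** Section 9.2.7 states: "Analyses of PK and immunogenicity will be described in the SAP".

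**The concern.** The objective names a comparator, and the population defined for the endpoint excludes it. An analysis that follows Table 11 literally will report treatment-emergent ADA incidence for the two itepekimab regimens with no placebo column.

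That column is useful here. The protocol reports no treatment-emergent ADA in any completed clinical study (sections 2.3.1 and Table 1), so few true positives are expected. If a small number appear on itepekimab, the placebo arm, followed over the same visits with the same assay, is the concurrent post-baseline reference for positives that have nothing to do with the drug. Table 1 also lists correlating ADA status with safety data among its mitigation measures for hypersensitivity, so how a positive result is read has some practical use beyond the endpoint itself.

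**Working it through.** No stated figure is in dispute. The check is a comparison of four elements of the protocol, followed by a count by arm.

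**Side by side**

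| Element | Where | Placebo included? |
|---|---|---|
| Objective | Synopsis; Table 2 | Yes, named as comparator |
| Sample collection and testing | Section 8.9; Schedule of Activities | Yes, all participants |
| Safety population | Table 11 | Yes, any randomised participant with at least one dose |
| ADA population | Table 11 | No |

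The first three agree and the fourth does not. No other population is named in the protocol for the ADA endpoint.

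**Could another clause bring placebo back in?**

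1. The instruction to analyse by the intervention actually received operates inside a population already limited to itepekimab-treated participants. There it only separates Q2W from Q4W.
2. Section 9.2.1 makes analyses by intervention group the default unless otherwise specified. In the ADA population the placebo group is empty by definition, so the default has nothing to display for it.
3. Section 9.2.7 leaves the immunogenicity analyses to the SAP. It does not leave the population open, because Table 11 has already fixed it.

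**Count by arm**

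Inputs from section 9.4: "Approximately 210 participants will be randomized in 1:1:1 ratio to investigational intervention groups", which is about 70 per group.

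- ADA population as written: at most 2 × 70 = 140, of whom 0 are on placebo.
- Left out by definition: 70 / 210 = one third of those randomised, which is the whole comparator.
- ADA population without the restriction: at most 3 × 70 = 210, including about 70 on placebo.

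These are upper limits, because membership also requires at least one dose and at least one post-baseline ADA result.

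**The case against.** The strongest reply is that nothing is lost. Placebo samples are drawn and tested, placebo participants are in the safety population, section 9 describes itself as a summary, and the SAP, which is not at hand, may tabulate placebo ADA results there. No sentence in the protocol says that placebo results will go unreported. This stands, and it limits the point. A reader might infer that the objective cannot be answered at all, but the documents support only that it cannot be answered in the ADA population as defined. It remains true that an SAP supplying the placebo column would have to use a population other than the one Table 11 sets for ADA.

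A reader might also infer that placebo is the sole source of information within the study on background assay reactivity. That is not so. The Week 0 sample is taken before dosing in all three arms and shows reactivity in serum not yet exposed to the drug. Section 8.9 also describes a validated assay with screening, confirmation and titre steps. What placebo adds is background after baseline, over the same follow-up.

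It would be tempting to put a number on the background positives that an active-only table might show. The protocol gives no background rate, and its report of no treatment-emergent ADA in completed studies gives no support for assuming one of any size. Nor does it contain a rule attributing every positive on itepekimab to the drug. The contradiction needs no such figure.

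Finally, an active-only ADA population can be a legitimate choice, and changing the objective would reconcile the text just as well. That is correct and is reflected in the fix.

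**Conclusion.** The point holds as an internal contradiction. The objective and the sampling plan include placebo; the ADA population excludes it. As written, that population contains at most about 140 of about 210 participants and no placebo participants, so the comparison named in the objective cannot be made in it. The counts rest only on the planned 1:1:1 allocation and about 70 per arm.

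The consequence is small. The endpoint is a descriptive secondary one. The co-primary analyses, the Type I error control, the sample size and the data collected are unaffected, and the placebo results will exist whichever way Table 11 reads. It is worth correcting because the correction costs almost nothing and lets the trial report on its own stated objective without departing from its own population table.

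**What to change.** Preferred: in the ADA row of Table 11, strike the three-word restriction to itepekimab-treated participants, so that the population is every safety-population participant with at least one post-baseline ADA result. Summarise treatment-emergent ADA incidence by actual treatment for Q2W, Q4W and placebo. This keeps the stated objective, gives the ADA row the same form as the PK row, and uses samples already planned.

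If an active-only ADA population is intended, there are two consistent alternatives:

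- keep Table 11 and state that the placebo ADA tabulation is made in the safety population; or
- keep Table 11 and remove the placebo comparison from the objective in both the synopsis and Table 2.

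Any of the three is a short text edit, to be carried into the SAP. None needs new samples, visits or participants.
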